6.2 Patient Identification and Randomization

The Informed Consent Form (ICF), signed prior to any study specific screening procedures being completed, will provide details on both the Screening Phase and the Active Phase of the study. Each patient that signs Informed Consent will be randomized to the active allograft, placebo, or conservative care treatment group. The randomization will occur through a secured envelope system, during which the subject will be provided with a unique subject identification number (XX-XXX, site number-subject number). During the Screening Phase, all subjects randomized to active allograft or placebo treatment will be scheduled for a transplantation procedure, while the conservative care treatment subjects will be followed as per the routine standard of care.

CONFIDENTIAL	Clinical Protocol	DATE	Р	age
		9Dec2019		
Patients with Low Back Pain with	mented Disc Regeneration in the $\underline{\mathbf{T}}$ reatment of the or without Intervertebral Disc Herniation –	WRITER TG, DB, PW	NO. 26	REV 6
VAST-001-017				

On or before Day 0 of the Active Phase, the patency of the affected disc will be confirmed, and subjects determined eligible from the screening phase who have consented to participation and are randomized to allograft treatment will receive the study material. Patients are considered enrolled in the study when they undergo successful treatment in the Active Phase and receive either allograft treatment, placebo (saline) treatment, or conservative care treatment.

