6.8 Treatment compliance

A lack of compliance during the Screening Phase will result in an exclusion from the Active Phase of the study. Once treatment occurs, a subject can only be excluded from the study due to the following:

- 1. Withdrawal of consent
- 2. Lost- to follow-up
- 3. Death
- 4. Subject undergoes subsequent surgery on the treated disc
- 5. Investigator withdrawal due to subject's study compliance

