6.10 Subject Withdrawal and Replacement

Subjects may withdraw from the study at any time without penalty and for any reason without prejudice to their future medical care. In all cases, the reason(s) for withdrawal, and the primary reason, must be recorded on the appropriate case report form (CRF). If a subject is prematurely withdrawn from the study after randomization (Day 0 of the Active Phase), the investigator must document the reason(s) and make every effort to perform a final Termination Visit. The procedures to be followed for the Termination Visit are the same as those defined for the Month 12 Visit.

Subjects that are consented, screened and randomized, but do not undergo a successful transplantation (Day 0 of the Active Phase) will be considered screen failures. These randomization assignments will be re-used. The randomization and the replacement of subjects will be orchestrated through a 3rd party designated independent of the data collection or analysis.

CONFIDENTIAL	Clinical Protocol	DATE	Р	age
		9Dec2019		
Patients with Low Back Pain with	mented Disc Regeneration in the $\underline{\mathbf{T}}$ reatment of th or without Intervertebral Disc Herniation –	WRITER TG, DB, PW	NO. 29	REV 6
VAST-001-017				

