8.4 Study Procedure

On Day 0 of the Active Phase, eligible subjects will undergo transplantation of supplemental allograft, or saline (placebo), or continue active standard of conservative care. This conservative care procedure will not be defined by this protocol however standard practice is to be followed by each physician. All subjects who undergo successful treatment will continue in the study and be followed as per the standard of care. Subjects randomized to continuing conservative care will be assessed at 3 months, and clinical indices will be assessed. These conservative care subjects who have experienced a significant decline in condition defined as a 10% increase in pain by VASPI, or a 9-point increase in ODI will be offered the allograft as a crossover. If the subject does not meet the aforementioned changes in ODI or VASPI, or is considering withdrawal, they may be offered the allograft treatment by physician discretion if condition has significantly declined.

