8.4.1 Transplant of supplemental allograft into the affected disc

All subjects randomized to active allograft will undergo an intervertebral lumbar injection into the target disc. The procedure of injecting the intervertebral disc will involve placing a 22-gauge needle into the center of the affected intervertebral disc. No contrast will be used prior to the injection of the supplemental allograft and 1mL of cells (approximately 6*10⁶ cells) mixed in a 1:1:0.75 by-volume ratio (Cells in cryoprotectant: Saline: NP) will be injected into the center of the affected disc(s) in the location of the nucleus pulposus. At least 1.5-2 milliliters of the resulting mixture will be available for injection into the nucleus pulposus of the symptomatic disc. Volume injected will be recorded.

Vital signs will be recorded prior to injection. The treatment injection should be carefully controlled. The injection procedure MUST be stopped if any of the following occur:

- The investigator cannot accurately place the needle tip in the nucleus pulposus
- The subject becomes hemo-dynamically unstable during the injection procedure.

CONFIDENTIAL	Clinical Protocol	DATE	P	age
		9Dec2019		T
TITLE: V iable A llograft S upplemented Disc Regeneration in the T reatment of		WRITER	NO.	REV
Patients with Low Back Pain wit	th or without Intervertebral Disc Herniation –	TG, DB, PW	36	6
VAST-001-017				

The following information regarding the treatment procedure must be documented:

- Procedure start and stop time
- Treatment administration stop time
- Treatment interruption information, if applicable
- Total volume of treatment injected
- Pain on implantation
- Anesthesia type(s)

The information collected above will also be collected during the placebo cross over visit.

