	mented Disc Regeneration in the $\underline{\mathbf{T}}$ reatment of th or without Intervertebral Disc Herniation –	WRITER TG, DB, PW	NO. 38	REV 6

- MRI evaluating the intervertebral height, adjacent endplates, deprivation of fluid and Pfirrmann score will be obtained during the Screening Phase and in the 2 weeks prior to transplant, and in the Active Phase at 12 months. Subjects will be randomized, yes or no (1:1 ratio), to receive an MRI at 6 months. Conservative care subjects that crossover to the allograft treatment group will all receive an MRI at 6-month follow-up after allograft treatment.
- X-rays will be performed static (standing), anterior-posterior and lateral in the Screening Phase prior to transplant. After transplantation, during the Active Phase (Months 6, and 12) a static and an additional dynamic (flexion/extension) X-rays will be performed.
- Adverse Events (AEs) and Serious Adverse Events (SAEs) will be recorded once the
 patient is enrolled (Day 0 of the Active Phase). A detailed discussion of AEs and SAEs is
 located in Section 14. Optional checkup evaluations will be performed in the case of
 complications. Failure of treatment defined as the necessity of a follow-up operation
 will be documented separately.
- Laboratory investigation will be conducted according to the routine procedures of each investigational center. The valid normal ranges including the methods for all parameters will be provided to the sponsor prior to the start of the study. Only laboratory values outside the normal range will be evaluated and commented upon by the investigator. The following parameters will be determined:

Hematology: Clinical Chemistry:

- hemoglobin - creatinine

- hematocrit - alkaline phosphatase

- erythrocytes - AST/SGOT - leukocytes - ALT/GPT - thrombocytes - γ -GT

- erythrocyte sedimentation rate - glucose

Coagulation:

- PTT

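### Conflicting enrolment rules allow a started-then-stopped injection to be classed as a screen failure, so an acute adverse event can go unrecorded or drop out of the safety results

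*Protocol*

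**What the plan says.** The protocol has two enrolment rules.

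- Protocol 6.2: "Patients are considered enrolled in the study when they undergo successful treatment in the Active Phase".
- Protocol 16, followed by SAP 6.1: the patient is enrolled once consent, screening and the eligibility check are complete, which is before any needle is placed.

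These sections decide what happens to a patient whose injection does not go to plan:

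- **Protocol 6.10.** Randomised subjects who "do not undergo a successful transplantation (Day 0 of the Active Phase) will be considered screen failures". It adds: "These randomization assignments will be re-used".
- **Protocol 8.4.** "All subjects who undergo successful treatment will continue in the study and be followed as per the standard of care".
- **Protocol 8.4.1.** The injection must be stopped in two situations. One is inaccurate needle placement. The other is: "The subject becomes hemo-dynamically unstable during the injection procedure". The site also records the volume injected and "Treatment interruption information, if applicable".
- **Protocol 8.5.** AE and SAE recording starts once the "patient is enrolled (Day 0 of the Active Phase").
- **Protocol 14.1 and 14.4.** Adverse events in the Screening Phase are not collected.
- **Protocol 6.8.** "Once treatment occurs, a subject can only be excluded from the study due to the" five listed reasons. An incomplete injection is not among them.
- **SAP 6.4.** The safety population is the ITT subjects who underwent treatment. Partial or stopped injections are not mentioned.

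Neither document says what makes a treatment or transplantation successful.

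**The concern.** Consider a patient whose injection has begun and who then becomes haemodynamically unstable. That instability is itself an acute adverse event, and it is also what forces the stop. If the stop makes the transplantation unsuccessful, 6.10 relabels the patient a screen failure and gives the slot to someone else. The event that should be reported can thus trigger the rule that removes the patient.

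Three things are at stake.

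- **Knowledge of a new product.** Safety is part of the primary objective (Protocol 9.1), and Protocol 12 acknowledges that there are no clinical data for this product in this population. A stopped injection is a likely place to see an acute reaction or a needle injury.
- **A fair comparison.** SAP 9.2 compares AE and SAE rates across the three arms. At the randomised procedure, the stop rule and the screen-failure rule can act only in the two injection arms. Any loss would make injection look safer relative to conservative care.
- **Care of the patient.** Protocol 14.4 follows an adverse event once it is known. A screen failure is not on the visit schedule, so a later effect of a partial dose, such as an infection or immune response, has no planned visit at which to be found.

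The point concerns safety capture and follow-up. It does not concern the efficacy populations.

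**Working it through.** The plan gives no figure on this point, so there is none to reproduce. The check sets the rules side by side for one case: the injection is started on Day 0 and stopped under 8.4.1.

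| Question | Reading that loses the event | Reading that keeps it |
|---|---|---|
| Is the patient enrolled? | No: treatment was not successful (6.2) | Yes: eligibility was confirmed (Protocol 16, SAP 6.1) |
| Status after the stop? | Screen failure, slot re-used (6.10) | Treatment occurred, and incompleteness is not a listed reason for exclusion (6.8) |
| Is the event recorded? | No: recording starts at enrolment (8.5, read with 6.2), and screening events are not collected (14.1, 14.4) | Yes: 8.5 equates enrolment with Day 0; Appendix A has adverse events at VA1; 14.1, 14.4 and 17.1 ask for events, SAEs and allograft complications |
| Is the patient followed? | No: 8.4 keeps those successfully treated | Yes, if 6.8 governs |
| In the safety population? | No, if a stopped injection is not counted as treatment (SAP 6.4) | Yes, if a partial dose counts (SAP 6.4) |

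Every step in the middle column rests on current text. So does every step in the right-hand column. Two sites could handle the same patient differently, and each could cite the protocol.

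**Effect of one or two lost cases**

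Inputs:

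- Planned allograft arm: 140 (Protocol Synopsis, SAP 4).
- Because 6.10 re-uses the assignment, the arm still fills to 140. One lost patient is the 141st and two make 142.

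Formula: the exact (Clopper-Pearson) two-sided 95% upper limit for k events in n patients is the 0.975 quantile of a Beta(k + 1, n − k) distribution. For k = 0 this is 1 − 0.025^(1/n).

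- Reported 0/140: 1 − 0.025^(1/140) = 2.6%.
- True 1/141 (0.7%): Beta(2, 140) quantile = 3.9%.
- True 2/142 (1.4%): Beta(3, 140) quantile = 5.0%.

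One omission changes none observed to one observed and raises the upper limit by about half (3.9/2.6 = 1.5).

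**How often an injection might be stopped**

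The documents give no rate, so the rates below are assumptions. With 140 + 40 = 180 planned injections, the expected number of stops is 180r and the chance of at least one is 1 − (1 − r)^180.

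| Assumed stop rate r | Expected stops | Chance of at least one |
|---|---|---|
| 0.5% | 0.9 | 59% |
| 1% | 1.8 | 84% |
| 2% | 3.6 | 97% |
| 5% | 9 | over 99% |

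These are stops, not lost events. A stop for needle placement may involve no adverse event, and a stop with an event may still be recorded.

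**The case against.** The best reply is that most of the safety text favours capture. Section 8.5 gives its own meaning of enrolment in the same sentence, namely Day 0, and a stopped injection happens on Day 0. Appendix A schedules adverse events at that visit. Section 14.4 requires every SAE during the study to be reported within 24 hours, with no condition on enrolment or success, and 15.7 repeats the duty. The SAP counts the patient as ITT and asks only that treatment was undergone, not completed. Section 8.4.1 expects interruptions and records them, so a stopped injection need not be an unsuccessful transplantation. For subjects withdrawn after randomisation, 6.10 also asks for a Termination Visit with the Month 12 procedures, and the Synopsis lets physicians recall subjects for safety at any time.

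Much of this stands. Loss is not certain. An SAE is better protected than a non-serious event and should normally reach the sponsor, in which case the remaining risk is its omission from the safety table under SAP 6.4. The limits above show the effect of an assumed loss and are not evidence that one occurred.

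It does not remove the problem. None of these provisions overrides the screen-failure sentence in 6.10. The Termination Visit is a single exit visit for withdrawn subjects, and it is arguable whether it applies to someone reclassified as a screen failure. Recall at a physician's discretion is not a schedule. Section 17.1 sends allograft complications to the sponsor but does not place them in the adverse event dataset or mention saline. Section 6.8 does not say whether a partial injection is treatment, and neither does SAP 6.4.

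**Conclusion.** The concern holds. The rules conflict, and one permitted reading classes a patient with a started and stopped injection as a screen failure, ends scheduled follow-up and leaves the event out of the record or the safety analysis. The text does not clearly require that result.

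The number of events affected is unknown and may be zero. If one allograft case of a given event is lost, a reported 0/140 (upper limit 2.6%) stands in place of 1/141 (3.9%); with two it stands in place of 2/142 (5.0%). This assumes that the arm fills to 140, that the slot is re-used, and that a site follows 6.2 and 6.10. Any loss would favour the injection arms over conservative care. The point should be fixed because the remedy is cheap and safety is a primary objective.

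**What to change.** - **Protocol 6.2, Protocol 16 and SAP 6.1:** use one enrolment definition.
- **Protocol 8.5 and 14.1:** collect AEs and SAEs from the start of the Day 0 procedure (needle insertion), or from Day 0 for conservative care, whether or not the injection is completed.
- **Protocol 6.10:** limit screen-failure status and re-use of assignments to subjects in whom no procedure was started.
- **Protocol 8.4:** follow every started injection for safety on the normal visit schedule.
- **SAP 6.4:** define the safety population as all randomised subjects in whom the procedure was started or who were assigned to conservative care. List stopped injections with the volume and interruption data that 8.4.1 already collects.

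The cost is protocol and SAP wording and safety follow-up of a few more patients. The listing needs no new data item. Reported adverse event rates may look slightly less favourable.

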6.3 Blinding

The assignment to treatment (active allograft, or placebo, or conservative care) is open label at Day 0 of the Active Phase to the extent that subjects receiving allograft or placebo will not be aware of what they have received, while those assigned to conservative care will be aware. All site study staff will be aware of the group to which each subject is randomized. Sites will be trained to ensure that subjects receiving the allograft or placebo treatment will remain blinded to their treatment throughout the study duration. Subjects will be unblinded during the study exit or upon signing of the new informed consent for the study extension.

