15.5	Site Initiation	49
15.6	Monitoring	50
15.7	Required Reports	50
16	STUDY REQUIREMENTS	52
16.1	Quality Assurance	52
16.2	Monitoring	53
17	PROCEDURES AND INSTRUCTIONS	55
17.1	Special safety-related procedures	55
17.2	Administrative procedures	55
17.3	Ethics and Good Clinical Practice	55
APPEND	DIX A - STUDY SCHEDULE	56
APPEND	DIX B- Supplemental TRANSPLANTATION /OTHER APPENDICES	58
APPEND	DIX C – Supplemental TRANSPLANTATION	59
REFEREI	NCE LIST	60

CONFIDENTIAL	Clinical Protocol	DATE	Р	age
		9Dec2019		T
	mented Disc Regeneration in the Treatment of the or without Intervertebral Disc Herniation –	WRITER TG, DB, PW	NO. 9	REV 6

STUDY CONTACTS

Sponsor: Vivex Biologics, Inc.

[name]

[contact]

Medical Monitor: H. [name]

Chief Medical Officer Vivex Biologics, Inc.

[contact]

Clinical Representative: [name]

Clinical Program Manager

Vivex Biologics, Inc.

[contact]

Principal Investigator: [name]

[name]

[name]

[name] [contact]

CONFIDENTIAL	Clinical Protocol	DATE 9Dec2019	P	age
	mented Disc Regeneration in the T reatment of the or without Intervertebral Disc Herniation –	WRITER TG, DB, PW	NO. 10	REV 6

PROTOCOL SYNOPSIS

Title	Viable Allograft Supplemented Disc Regeneration in the Treatment of Patients with Low Back Pain with or without Intervertebral Disc Herniation – VAST Trial
Objective	To evaluate the safety and efficacy of viable allograft transplantation for the treatment of patients with symptomatic disc degeneration and tissue loss
Study Design	Multi-center, prospective, parallel, triple arm study to assess patients who participated in the VAST trial and receiving either viable allograft, saline, or allograft after cross-over. These patients will be evaluated at baseline, injection, 6 months, and 12 months. Subjects will then have an option for a 24 months and 36 months extension after their index procedures. Patients who received saline or active allograft in the VAST study, will be allowed to receive viable allograft and followed for an additional 12 and 24 months after that election. These subjects will need to meet initial inclusion/exclusion criteria again before another injection.

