Endpoints	 Primary: Improvement in Oswestry Disability Index (ODI) at 6 and 12 months after treatment. Durability of Oswestry Disability Index (ODI) at 24 and 36 months after initial inclusion compared with 12 month improvement. Improvement in Visual Analogue Scale of Pain Intensity (VASPI) at 6, and 12 months after treatment. Durability of Improvement in Visual Analogue Scale of Pain Intensity (VASPI) 24 months and and 36 months after initial inclusion compared with 12 month improvement.
	Secondary Page 10 of 62

CONFIDENTIAL	Clinical Protocol	DATE	P	age
		9Dec2019		
	mented Disc Regeneration in the $\underline{\mathbf{T}}$ reatment of th or without Intervertebral Disc Herniation –	WRITER TG, DB, PW	NO. 11	REV 6

	 Improvement in ODI, SF-36, and VASPI at 6 and 12 months after treatment Improvement in ODI, SF-36, and VASPI scores for optional 24 month and 36 month follow up subjects X-ray and MRI measurements at 6 and 12 months after treatment AE/SAE rates after treatment Hospitalization rate at 12, 24, or 36 months after treatment Re-operation rate at 12, 24, or 36 months after treatment Resource utilization following treatment and at 6 and 12 months (and optional 24 & 36 month) follow up visits 		
Study Population	Patients evaluated for degenerative intervertebral disc disease demonstrating Pfirrmann Grade [3-6] by MRI		
Clinical Sites	Up to twenty (20) sites in the United States		
Sample size and	Approximately 220 subjects randomized to viable allograft or placebo or control in 3.5:1:1 ratio:		
randomization	$n_{active} = 140$ $n_{placebo} = 40$ $n_{control} = 40$		
	For study extension: The original randomized population will be pooled and reconsented for an optional follow up for 24 and 36 months.		
Study Design	The study is composed of three separate phases. There will be the Screening Phase followed by the Active Phase equaling 12 months then followed by the optional long term follow up at 24 months and 36 months. Patients need to meet entry criteria for all phases.		

CONFIDENTIAL	Clinical Protocol	DATE 9Dec2019	Р	age
	mented Disc Regeneration in the T reatment of the or without Intervertebral Disc Herniation –	WRITER TG, DB, PW	NO. 12	REV 6

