CONFIDENTIAL	Clinical Protocol	DATE	Р	age
		9Dec2019		T
TITLE: V iable A llograft S upplemented Disc Regeneration in the T reatment of		WRITER TG, DB, PW	NO.	REV
Patients with Low Back Pain with VAST-001-017	th or without Intervertebral Disc Herniation –	. 0, 22,	31	6

7.1.6 Active Phase Month 12 (+ 30 days) or VA5:

All randomized subjects will return to the clinic 12 months (+ 30 days) subsequent to transplantation for safety and efficacy assessments as outlined in Appendix A. ODI, VASPI, and SF-36 questionnaires will be completed by the subject, with assistance from physician or physician designee. All subjects will receive an MRI and X-ray at the 12-month follow-up visit. A review of resource utilization through the 12 Month visit will be completed.

7.1.7 Optional Long-Term Follow Up Month 24 & Month 36 (+ 3 Months) or VA6 & VA7:

All randomized subjects will have an option to continue to be monitored for long-term follow up. Before study procedures begin, the informed consent addendum 2 for study extension will need to be signed. At the 24-month in-office visit, subjects will first be reevaluated for inclusion/exclusion and fill out VASPI, ODI, SF-36, and Resource Utilization. If eligible for allograft treatment, the PI will perform a neurological exam, physical exam, labs, and give the subject applicable questionnaires. All randomized subjects will have the option to receive allograft treatment at 24 months in accordance with the inclusion/exclusion re-evaluation. An MRI and x-ray will be performed on subjects receiving another injection for safety purposes. If needed, a second office visit may be scheduled within 14 days of the original evaluation to allow appropriate time for the laboratory investigation and MRI. All follow up subjects will complete VASPI, ODI, SF-36, and Resource Utilization questionnaires at both follow up visits. The 36-month will consist of questionnaires and can be performed over the phone if the subject chooses.

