8 INCLUSION / EXCLUSION CRITERIA

8.1 Inclusion Criteria

Patients will be entered into this study only if they meet ALL of the following criteria:

- Able to provide an English written Informed Consent
- Age 18 to 60 years inclusive
- Male or female
- Body mass index <35
- Pfirrmann Grade [3-6]
- Radiographic confirmation by MRI/X-ray of:
 - (1) translational instability defined as ≤5 mm, or
 - (2) angular instability defined as ≤5°
- Back pain (with or without radicular leg pain) measured by:
 - (3) ODI of at least 40%, and
 - (4) VASPI of at least 40mm
- Pathologic level between L1 and S1
- 1 or 2 vertebral level involvement that has been evaluated for at least 6 months and treated with conservative care
- Symptomatic back pain attributable to intervertebral disc for a minimum of 6 months
- No previous surgical treatment at the disc level(s) being considered
- Psychosocially, mentally and physically able to fully comply with this protocol, and follow-up schedule
- Ability to undergo allograft transplantation
- Life expectancy >2 years
- No contraindications to MRI
- No history of malignancy (basal cell carcinoma) or chronic infectious disease (e.g. HIV, Hepatitis)
- Agree to use appropriate contraception; not planning on becoming pregnant for 24 months after treatment
- Patient disc for transplant confirmed by inter-discal pressure measurement, or disc-imaging study.
- No signs or symptoms of infection
- No chronic use (>7 consecutive days) of anticoagulants (such as aspirin) or NSAIDs prior to treatment

CONFIDENTIAL	Clinical Protocol	DATE	P	age
		9Dec2019		
	mented Disc Regeneration in the $\underline{\mathbf{T}}$ reatment of th or without Intervertebral Disc Herniation –	WRITER TG, DB, PW	NO. 34	REV 6

8.2 Exclusion criteria:

- Seropositive or seronegative spondyloarthropathy
- Type III Modic changes
- Prior surgeries of segments between L1 and S1
- Chemonucleolysis or percutaneous laserectomy of the affected disc prior to the study
- Chronic facet syndrome
- Stenosis of the spinal canal that is moderate to severe or more in degree
- Spondylodiscitis
- Spondylolisthesis (lysis and degenerative)
- Severe motor deficit or cauda equina disorder based on investigator determination
- Congenital abnormalities of the spinal nerves
- Pelvic and inguinal angiopathy
- Neurogenic inguinal syndrome
- Syringomyelia
- Diastenomatomyelia
- Traumatic neurological disorders
- Diseases of the kidney (nephritis, pyelonephritis)

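### Patients are unblinded on signing the extension consent, before the 24-month ODI, VASPI and SF-36 are completed, so the durability comparison is open to reporting bias of unknown size and direction

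*Protocol*

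**What the plan says.** Five statements in the protocol combine.

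- **Unblinding.** Section 6.3: "Subjects will be unblinded during the study exit or upon signing of the new informed consent for the study extension". The same section says that site staff know every patient's group, so only allograft and saline patients are blinded.
- **Consent first.** Section 7.1.7: "Before study procedures begin, the informed consent addendum 2 for study extension will need to be signed". Appendix A marks informed consent at VA6, the 24-month visit.
- **Then the forms.** Section 7.1.7: "At the 24-month in-office visit, subjects will first be reevaluated for inclusion/exclusion and fill out VASPI, ODI, SF-36, and Resource Utilization". Appendix A schedules one ODI and one VASPI at VA6.
- **Access to a further injection.** Section 7.1.7: "All randomized subjects will have the option to receive allograft treatment at 24 months in accordance with the inclusion/exclusion re-evaluation". The synopsis (Study Design) adds: "These subjects will need to meet initial inclusion/exclusion criteria again before another injection". The criteria in 8.1 include an "ODI of at least 40%, and" a VASPI of at least 40 mm.
- **Use of the scores.** The synopsis lists under Primary: "Durability of Oswestry Disability Index (ODI) at 24 and 36 months after initial inclusion compared with 12 month improvement", with a matching line for VASPI. It also says that the randomized population is pooled for the extension.

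The SAP places its final analyses after the last 12-month visit and contains no 24- or 36-month analysis.

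**The concern.** ODI and VASPI are self-reported and site staff know the allocation, so the patient's own blinding is the only blinding these outcomes have. The written sequence removes it just before the 24-month measurement. Durability then sets scores given without knowledge of the arm (month 12) against scores given with it (month 24). A change between the two visits could reflect the disc, the disclosure, or both.

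There is a second pressure on the same answers. A patient who wants an injection has reason to report at least 40 on both scales, and no separate eligibility score is named. VA6 is also the last visit before any 24-month injection, so weak measurement there cannot be fully recovered later.

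**Working it through.** **Order of events at VA6 as written**

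| Step | Event | Source |
|---|---|---|
| 1 | Addendum signed | 7.1.7; Appendix A, VA6 |
| 2 | Assignment disclosed | 6.3 |
| 3 | Eligibility re-check; ODI, VASPI, SF-36 completed | 7.1.7; Appendix A, footnote f |
| 4 | Injection if criteria are met again | Synopsis; 7.1.7; 8.1 |

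Nothing in either document offsets this. There is no questionnaire before disclosure and no sensitivity analysis for it.

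That the scores in step 3 decide step 4 is an inference. It rests on the initial criteria applying again, their ODI and VASPI thresholds, and the single collection at VA6. Section 7.1.7 also mentions further questionnaires for eligible patients without naming them.

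**Duration wording.** Section 6.3 wants allograft and saline patients kept blinded for as long as the study lasts. Section 6.9 gives 12.5 months for screening plus active phase, then a total that includes the extension: 12.5 + 24 + (3 to 6) = 39.5 to 42.5 months. Under the second figure, 6.3 contradicts itself.

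**Size.** The plan gives no figure for the 24-month comparison, so there is nothing to reproduce. From the documents: ODI SD 15.5, minimum important difference 6, target difference 9 (13.3); arms of 140, 40 and 40 (synopsis). The shifts below are assumptions, as is equal extension uptake in the three arms. Higher ODI is worse.

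*Pooled mean.* Let s be the reporting shift in points:

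- saline scores s higher, others unchanged: pooled shift = (40/220)s
- saline and allograft both score s higher: (180/220)s
- saline scores s higher, allograft s lower: ((40 - 140)/220)s

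| s | Saline only | Both higher | Opposed |
|---|---|---|---|
| 2 | +0.4 | +1.6 | -0.9 |
| 3 | +0.5 | +2.5 | -1.4 |
| 4 | +0.7 | +3.3 | -1.8 |
| 6 | +1.1 | +4.9 | -2.7 |

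The first two columns understate durability and the third overstates it. The spurious saline-minus-allograft difference is s, 0 and 2s respectively.

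*Arm comparison, if one were made at month 24.* With no true difference and a saline-only shift s, the chance of p<0.05 is about Phi(s/SE - 1.96), with SE = 15.5 × sqrt(1/140 + 1/40) = 2.78. For s = 3: Phi(1.08 - 1.96) = 19%. For s = 2, 4 and 6 it is 11%, 30% and 58%. With half retained (70 v 20), s = 2, 3, 4 and 6 give 7%, 12%, 17% and 33%.

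*Threshold seeking.* A uniform shift is a crude model of this, because the incentive acts mainly on patients just below 40. Suppose true ODI is normal with mean 25 to 40 and SD 15.5, and that 25% to 100% of patients within 6 to 15 points below 40 report 40. The arm mean then rises by 0.1 to 2.8 points. The share at or above 40 moves more. With mean 30, a 9-point band and half of those patients, it goes from 25.9% to 25.9% + 0.5 × (47.4% - 25.9%) = 36.6%. This is the share passing the ODI cut-off alone, not an eligibility rate, since VASPI and all other criteria also apply.

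**The case against.** A reader might infer that the order biases the data in favour of allograft, because saline patients score high once they know their arm. The documents do not support a direction. Allograft patients may also be injected at 24 months under the same criteria, so both blinded arms share the threshold incentive. The synopsis defines durability against the 12-month result in a pooled population, not as a contrast between arms. This objection stands, and the sign changes in the table above show it.

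A reader might also infer that VA6 gives the only clean durability data. It does not: the 24-month injection is optional, and patients who decline it or do not qualify give 36-month scores with no 24-month injection in between. VA6 is the last point before possible re-injection for all who are followed.

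Other points that stand:

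- The SAP's co-primary endpoints are at 12 months, and protocol section 6 describes the extension as optional with additional secondary endpoints. No confirmatory result depends on VA6.
- Conservative care was never blinded, so the loss concerns two of three arms.
- Patients unblinded at a 12-month study exit who later join the extension already know their arm. Reordering VA6 does not help them.
- Reordering leaves the same scores as outcome and eligibility check. A blinded patient who wants allograft still has reason to score high.

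None of these explains why disclosure should come before the forms.

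**Conclusion.** The point holds as a limited, cheaply corrected weakness. Unblinding before the 24-month forms is explicit in the text; the dual use of the scores is a reasonable inference. The comparison of 24-month with 12-month scores is open to reporting bias. Its size and net direction cannot be derived: every figure above rests on assumed shifts, means and uptake, and shows only that shifts below the trial's 6-point minimum important difference could matter.

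A reader might go on to doubt the primary result. Consent signed at VA6 comes after the 12-month forms, so that does not follow. Section 6.3 does not say whether study-exit unblinding comes after those forms. That is a gap to close, not evidence that it comes before.

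The synopsis says that entry criteria must be met for all phases, which could be read as making follow-up itself depend on scores of at least 40. Section 7.1.7 suggests that only the injection is so restricted, and the text should settle this.

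**What to change.** Amend 6.3 and 7.1.7 so that, at VA6, the patient signs the addendum, completes the ODI, VASPI and SF-36, the forms are locked, and only then is the assignment disclosed. In addition:

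- State in 6.3 that any study-exit unblinding follows completion of the 12-month forms.
- Record the date of disclosure for each patient, flag those unblinded before their VA6 forms, and report their durability data as open-label.
- Reconcile the blinding period in 6.3 with the duration in 6.9. Also reconcile 6.4, which names saline and allograft patients as eligible for the 24-month injection, with 6.9 and 7.1.7, which name all randomized subjects.
- State whether the VA6 scores are the eligibility scores. If they are, report the 24-month results with that limitation, since the reordering does not remove the incentive.

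The cost is a small protocol amendment with committee submission (15.1), a note to sites, and possibly a change to the addendum wording. It needs no extra visit or procedure and changes no treatment or eligibility rule. It is a cheap improvement.
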